5.6.5 Electrocardiograms

12-lead ECG will be performed at the baseline and each postbaseline visit. The mean QTc Fridericia (QTcF) and other ECG intervals based on triplicate ECG will be obtained. Descriptive statistics for ECG parameters (QTc Bazett, QTcF, PR interval, QRS duration and RR interval) and changes from baseline will be presented by visit, subgroup and overall. Shift tables will present changes from baseline in ECG interpretation (categorized as normal; abnormal, not clinically significant; abnormal, clinically significant) to each post-baseline visit and to the end of treatment.

In addition, the number (percentage) of subjects with at least 1 postbaseline abnormal ECG result in QTc Fridericia during the treatment period will be summarized according to the following categories.

Clinically borderline or abnormal ECG results QTcF will be categorized as follows:

Absolute QTcF interval prolongation:

- QTcF interval >450 msec
- QTcF interval >480 msec
- QTcF interval >500 msec

Change from baseline in QTcF interval:

- QTcF interval increases from baseline >30 msec
- QTcF interval increases from baseline >60 msec

Plus at least one postbaseline QTcF interval >450 msec and increase from baseline >60 msec.

The number (percentage) of subjects, by subgroup and overall, with at least 1 postbaseline abnormal ECG results during the treatment period, Weeks 3, 6, 9 and 12 (and ED, as needed) will be summarized according to the following categories:

- QTcF prolongation by >60 ms from baseline and absolute QTcF >450 ms
- QTcF prolongation to >500 ms
- Change from baseline of PR $\geq 25\%$ to an absolute PR value of >220 msec
- Change from baseline of QRS $\geq 25\%$ to an absolute QRS value of >120 msec.

5.6.6 Other Safety Analyses

5.6.6.1 C-SSRS

The C-SSRS responses will be mapped to C-CASA as suggested by the C-SSRS Columbia website.

Number (percentage) of subjects with any treatment-emergent suicidal ideation, suicidal behavior, and suicidality (suicidal ideation and/or behavior) will be displayed. “Treatment-emergence” is used for any new or worsened events during the Treatment Phase (treatment and follow-up) compared with the baseline C-SSRS assessment. This will be produced for at any point during the study, and by visit.

Shift from baseline to the maximum suicidal ideation severity rating (0=no ideation present to 5=active ideation with specific plan and intent) during the Treatment Phase will assess worsening of suicidal ideation. Any score greater than 0 indicates the presence of suicidal ideation while a score of 4 (active suicidal ideation with some intent to act, without specific plan) or 5 (active suicidal ideation with specific plan and intent) can be used to indicate serious suicidal ideation.

5.6.6.2 MDS-UPDRS-III

Changes from baseline in the total score and four subscores of MDS-UPDRS-III will be summarized using descriptive statistics for continuous variable by visit and treatment group. No formal statistical analyses will be performed. Figures will be produced by visit, they will present without amyloid DLB, with amyloid DLB, without amyloid PDD, with amyloid PDD, with amyloid and without amyloid copathology (regardless of DLB/PDD).

This scale evaluates extrapyramidal features in motor function in Parkinson’s disease. It contains 33 items in 18 categories: (1) speech, (2) facial expression, (3) rigidity, (4) finger tapping, (5) hand movements, (6) supinational and pronation movements of hands, (7) toe tapping, (8) leg agility, (9) arising from chair, (10) gait, (11) freezing of gait, (12) postural stability, (13) posture, (14) body bradykinesia, (15) postural tremor of hands, (16) kinetic tremor of hands, (17) rest tremor amplitude and (18) constancy of rest tremor. Each item is scored 0 to 4, giving a total score range 0 to 132. As far as is practical, the motor assessments should be made with the subject in the “on” state at each visit and at the same time relative to the subject’s last dose of Parkinson’s disease medication (such as L-dopa).

The 4 subscores are for tremor, rigidity, bradykinesia and postural instability and gait difficulty (PIGD), as calculated per Section 8.5.

5.7 Other Analyses

Not applicable.

5.8 Exploratory Analyses

The exploratory efficacy endpoints, MoCA (and subitems), WAIS-IV DSC, CIBIC-Plus (and subitems), CGIC, CFI, MMSE, NPI (NPI-12, NPI-10, NPI-4 and NPI-D, and each subscore), SAPS-PD and FAQ, will be summarized based on the FAS, by subject subgroup (DLB without amyloid copathology, DLB with amyloid copathology, PDD without amyloid copathology, and PDD with amyloid copathology). No formal statistical analyses will be performed. Figures will be produced by visit, they will present without amyloid DLB, with amyloid DLB, without amyloid PDD, with amyloid PDD, with amyloid and without amyloid copathology (regardless of DLB/PDD).

The exploratory efficacy endpoint, MoCA will be repeated for subgroups as per Section 5.3.4.

6 INTERIM ANALYSES

No interim analyses are planned for this study.

7 CHANGES IN THE PLANNED ANALYSES

No changes have been made.

8 DEFINITIONS AND CONVENTIONS FOR DATA HANDLING

8.1 Efficacy data handling

8.1.1 Pretreatment/Baseline Efficacy

Baseline for all efficacy endpoints is defined as the last pretreatment assessment.

8.1.2 Treatment Duration for Efficacy Analyses

If additional data are collected other than scheduled visits, the additional data will be mapped to the closest scheduled visit if the data on this scheduled visit is missing.

Table 3 Mapping of Study Day Ranges to Week for Efficacy

Windowing Period	Study Day Range (Relative to First Dose)	Week
Screening	$(-42) \leq \text{Day} \leq (-8)$	
Baseline	$(-7) \leq \text{Day} \leq (-1)$	
Analysis Baseline	-	a
Treatment	$1 \leq \text{Day} \leq 63$	6 (d)
Treatment	$64 \leq \text{Day} \leq 98$	12 (d)
End of Treatment (EOT)	-	b
Follow up	Follow up visit	c

a: All pretreatment assessments are conducted during Screening/Baseline Periods before Day 1. The Analysis Baseline is the last non-missing value measured during pretreatment phase.

b: For completer, EOT is the Week 12 visit. For early discontinuation, EOT is the Early Discontinuation (ED) visit. If the above visits are missing, then the last non-missing value collected not later than 7 days after the last dose will be used.

c: If follow up visit is missing, there will be no imputed follow up visit. Unscheduled visits can be mapped to follow up for listings, but the CRF follow up visit will be used for analysis.

d: For assessments with no Week 6 planned assessment, the window for the Week 12 assessment is $1 \leq \text{Day} \leq 98$. The data must be within in the date of first dose and date of ED visit (for early discontinuation subjects). For completers, date of last dose is irrelevant, window the visit based on study day range in above table.

8.1.3 Efficacy Data Collected After the ED Visit

Subjects who discontinue study drug are expected to continue in the study for the originally scheduled visits, starting with next such visit that is after the ED Visit. The scheduled visits post ED will be flagged in the listings and datasets to reflect its post ED status.

8.2 PD data handling

8.2.1 Pretreatment/Baseline PD

Baseline for all PD endpoints is defined as the last pretreatment assessment.

8.2.2 Treatment Duration for PD Analyses

If additional data are collected other than scheduled visits, the additional data will be mapped to the closest scheduled visit if the data on this scheduled visit is missing.

Table 4 Mapping of Study Day Ranges to Week for PD

Windowing Period	Study Day Range (Relative to First Dose)	Week
Screening	$(-42) \leq \text{Day} \leq (-8)$	
Analysis Baseline	-	a
Treatment	$1 \leq \text{Day} \leq 98$	9

a: All pretreatment assessments are conducted during Screening before Day 1. The Analysis Baseline is the last non-missing value measured during pretreatment phase.

8.2.3 Duplicate PD Tests

The following rule will be performed if duplicate results are received on biomarker data, if back up samples are tested in addition to the primary samples:

- 1) Deviation between first and second result $\leq 15\%$. Accept first result.
- 2) deviation between first and second result $> 15\%$ and $\leq 30\%$. Report the mean of the first and second result.
- 3) Deviation between first and second result $> 30\%$. Present as missing data.

Deviation = $100\% * (\text{second result} - \text{first result}) / \text{first result}$

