9.5.1.3.2 PHARMACODYNAMIC, PHARMACOGENOMIC, AND OTHER BIOMARKER, ASSESSMENTS

Baseline Biomarker Assessments

A plasma sample will be collected during the Screening Period (Tier 3) to measure biomarkers related to AD copathology (including amyloid and p-tau) and other biomarkers related to DLB or PDD. These baseline plasma amyloid A β 42/A β 40 ratio will be used to classify subjects into the various categories (DLB without amyloid copathology, DLB with amyloid copathology, PDD without amyloid copathology and PDD with amyloid copathology). The baseline plasma biomarkers may also be used to define other subgroups classifications of subjects for subgroup analyses.

A CSF sample will be collected during the Screening Period (at least 7 days before the Baseline Visit) to measure baseline CSF cGMP and biomarkers related to DLB or PDD. These DLB or PDD related biomarkers may be used to define other subgroups classifications of subjects for subgroup analyses.

Plasma concentrations of A β 42 and A β 40 will be measured by the validated immunoprecipitation LC-MS/MS C2N Preclivity plasma assay. Plasma concentrations of p-tau 181, glial fibrillary acidic protein (GFAP), and neurofilament light (NFL) will be measured by Quanterix Simoa plasma assay.

CSF concentrations of cGMP will be measured using a validated assay. Other CSF biomarkers represented by A β 42, A β 40, tau, p-tau will be measured by Lumipulse platform and CSF NFL, neuregulin (NRG) will be measured by Simoa.

Pharmacodynamic Assessments

CSF samples will be collected during the Screening Period (at least 7 days before the Baseline Visit) and after 9 weeks on E2027. Both samples should be collected at approximately the same time in the morning, either in the fasted state (preferred) or at least 2 hours after breakfast. The CSF sample during the Treatment Period should be collected after the predose blood draw for PK and plasma biomarker analysis at the study visit after

9 weeks on E2027. The CSF samples will be assayed for cGMP and E2027. Other CSF biomarkers related to DLB or PDD or E2027 PD effects may also be assayed, if appropriate. CSF concentrations of cGMP and other biomarkers will be measured using validated assays.

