
5.2.4 Demographic and Other Baseline Characteristics and 5.3.4 Examination of Subgroups
 
Update to cutpoint for CSF Aβ42/40 ratio and CSF p-tau181/Aβ(1-42) ratio
	
In correct cutpoints were referenced. CSF Aβ42/40 ratio was changed from 0.0597 to 0.0571. CSF p-tau181/Aβ(1-42) ratio was changed from 0.0749 to 0.083.

5.3.4 Examination of Subgroups and 5.6.2 Adverse Events
 
Removal of subgroups for: On AChEI at baseline (Yes or No), Hoehn & Yahr stage (0&I&II or III), Baseline MMSE subgroup (\geq14 total score \leq19, \geq20 total score \leq26), Age ($<$65, \geq 65), NPI hallucination sub-item score (\geqmedian/$<$median), Caregiver's time per week to spend with subject (\geqmedian/$<$median).
	
Due to the number of subjects, it was not useful to subgroup the data in this detail.

8.2.3 Duplicate PD Tests
 
Wording added to implement derivation for any duplicate PD tests received.
	
Added for completion for derivation of a single value if duplicate tests received.

8.3.2 Treatment Duration for Safety Analyses
 
Footnote d added to Table 5
	
Footnote d added for clarity.

8.4 Algorithms for Efficacy Parameters
 
NPI total scores are set to zero if any part
	
To be consistent with the derivation from Study 201

is missing, changed from set to missing if any part is missing.	
---	--

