4 DETERMINATION OF SAMPLE SIZE

Assuming the standard deviation of percentage change from baseline in CSF cGMP at Week 9 was 60, the sample size of 6 completers per subgroup (for 8 enrolled subjects per subgroup, assuming a 25% dropout rate), would have approximately 80% power to detect the difference in change from baseline of CSF cGMP of 100% between the DLB without amyloid copathology subgroup and the DLB with amyloid copathology subgroup. The analysis between the PDD without amyloid copathology subgroup and the PDD with amyloid copathology subgroup, also would have approximately 80% power to detect the difference in change from baseline of CSF cGMP of 100% (same assumptions as above). These sample size calculations illustrated the possible differences that could be seen between subgroups. However, without previous data on the differences between subgroups in CSF cGMP, these were for illustration only and it was not expected statistical significance would be reached with 6 subjects per subgroup.

The probability of observing a difference in percentage of CSF cGMP between 2 subgroups (DLB without amyloid copathology subgroup minus DLB with amyloid copathology subgroup, or PDD without amyloid copathology subgroup minus PDD with amyloid copathology subgroup) $\geq 30\%$ depends on the true difference between the 2 subgroups. If the true difference was 100%, there would be 97.8% probability that the observed difference was $\geq 30\%$. If the true difference was 60%, the probability was 80.7%. If the true difference was 10%, there would be 28.2% probability that the observed difference was $\geq 30\%$.

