5.5.2 Pharmacodynamic, Pharmacogenomic, and Other Biomarker Analyses

Pharmacodynamic Analyses

The PD Analysis Set will be used for the summaries and analyses of CSF and plasma PD biomarkers. The percentage change from baseline in CSF cGMP at 9 weeks of treatment will be analyzed to compare different subject subgroups (DLB without amyloid copathology vs DLB with amyloid copathology, and PDD without amyloid copathology vs PDD with amyloid copathology). Secondary comparisons will be: total (DLB+PDD) without amyloid vs with amyloid, DLB without amyloid vs PDD without amyloid, and DLB with amyloid vs PDD with amyloid.

Analyses, comparing the different subgroups, of the percentage change from baseline in CSF cGMP will be performed using an analysis of covariance, where baseline CSF cGMP will be included as a covariate. The least square (LS) means, LS mean subgroup differences and 95% CIs will be presented.

The change from baseline in CSF cGMP at 9 weeks of treatment will also be analyzed. Other CSF and plasma PD biomarkers (CSF amyloid, plasma p-tau181, CSF p-tau181, plasma neurogranin, plasma neurofilament, CSF neurogranin, CSF neurofilament, etc) may be analyzed similarly, if appropriate.

The CSF and plasma PD biomarkers (both percentage change and change from baseline at 9 weeks) will be summarized by subgroups, as defined in section 5.3.4.

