9 PROGRAMMING SPECIFICATIONS

The rules for programming derivations and dataset specifications are provided in separate documents.

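### The duplicate-result rule in SAP 8.2.3 uses a signed deviation, so a second result far below the first never triggers averaging or exclusion

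*SAP*

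**What the plan says.** SAP 8.2.3 applies to biomarker data "if back up samples are tested in addition to the primary samples". It defines "Deviation = $100\% * (\text{second result} - \text{first result}) / \text{first result" and sets three tiers:

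- Tier 1: "Deviation between first and second result $\leq 15\%$. Accept first result".
- Tier 2: above 15% and up to 30%, report the mean of the two.
- Tier 3: above 30%, treat as missing.

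No tier has a lower limit. The Version 2 change table gives the reason for the section as "Added for completion for derivation of a single value if duplicate tests received". The protocol has no duplicate rule of its own. SAP section 9 says: "The rules for programming derivations and dataset specifications are provided in separate documents".

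SAP 5.2.4 lists CSF cGMP among the biomarkers, so the rule can reach the primary endpoint, the Week 9 percentage change in CSF cGMP. That endpoint is analysed by "analysis of covariance, where baseline CSF cGMP will be included as a covariate".

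**The concern.** The tiers exist to catch duplicates that disagree. As printed they catch disagreement in one direction only. A second result below the first gives a negative deviation, which satisfies the tier 1 condition however large the drop. The same two numbers are handled differently depending on which was reported first.

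If the two results are independent with equal error, the rule keeps high first results and averages or discards low ones, so the retained level is biased upward. For CSF cGMP this raises the percentage change when the Week 9 sample is duplicated and lowers it when the baseline is. With 6 completers planned per subgroup, one discordant value that is kept when the tiers were evidently meant to average or remove it can move a subgroup mean.

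**Working it through.** **Literal reading.** Concentrations are positive, so a fall can never exceed 100%. Every pair with the second result below the first has a deviation between -100% and 0, and falls in tier 1.

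| First, second | Signed deviation | As printed | With absolute value |
|---|---|---|---|
| 100, 90 | -10% | 100 | 100 |
| 100, 84 | -16% | 100 | mean 92 |
| 84, 100 | +19% | mean 92 | mean 92 |
| 100, 40 | -60% | 100 | missing |
| 40, 100 | +150% | missing | missing |

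Only pairs more than 15% down are affected. Pairs with the second result above the first are handled identically under both readings.

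**Assumptions for size.** The protocol says only "CSF concentrations of cGMP will be measured using a validated assay" and gives no assay CV; neither document counts duplicates. I assume both results are independent lognormal with the same mean and a CV of 5, 10, 15 or 20%. The figures come from numerical integration; a simulation of 4,000,000 pairs agrees to rounding. They do not apply if back-ups were run because a first result looked doubtful.

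| Assumed CV | 5% | 10% | 15% | 20% |
|---|---|---|---|---|
| Pairs more than 15% down | 1.1% | 12.5% | 22.1% | 28.1% |
| Pairs more than 30% down, kept as printed | 0.0% | 0.6% | 4.5% | 10.1% |
| At least one such pair in 6 duplicates | 0.0% | 3.4% | 24.3% | 47.4% |
| Bias in retained level, as printed | +0.2% | +1.7% | +3.6% | +5.7% |
| Bias in retained level, absolute value | +0.1% | +0.2% | 0.0% | -0.3% |

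The third row is 1 - (1 - p)^6, with p the unrounded value of the row above.

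**Subgroup contrast.** Take a true Week 9 to baseline ratio of 2.68 in one subgroup (the 168% mean rise reported for Study 201 in Protocol 7.2) and 2.38 in the other. The true contrast is 30 points, the difference discussed in Protocol 9.2. With equal duplication in both subgroups, the shift (as printed minus absolute value) in points is:

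| Samples duplicated | CV 5% | CV 10% | CV 15% | CV 20% |
|---|---|---|---|---|
| All Week 9 | 0.0 | +0.5 | +1.1 | +1.9 |
| All baseline | 0.0 | -0.4 | -0.9 | -1.5 |
| Both | 0.0 | 0.0 | +0.1 | +0.2 |

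The largest shift is 32.97 - 31.09 = 1.9 points. SAP section 4 states "Assuming the standard deviation of percentage change from baseline in CSF cGMP at Week 9 was 60", with 6 completers per subgroup, so the planned standard error of a difference is 60 × sqrt(2/6) = 34.6, and 1.9 / 34.6 = 0.05.

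**One subject (constructed).** Week 9 value 2.68; baseline results 1.00 then 0.72, a deviation of -28%.

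- As printed, baseline 1.00: 2.68 / 1.00 - 1 = +168%.
- With the absolute value, baseline (1.00 + 0.72) / 2 = 0.86: 2.68 / 0.86 - 1 = +211.6%.
- The difference is 43.6 points, or 43.6 / 6 = 7.3 in a mean of 6, which is 7.3 / 34.6 = 0.21 of the standard error.

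**The case against.** The tiers speak of a deviation between the two results and escalate from accepting to averaging to discarding. That makes sense only for a magnitude, so this is most likely a slip of notation, and the program may already use the absolute value. Nothing shows that any CSF cGMP sample was assayed twice. The larger figures need a CV of 15% to 20% and every sample at a visit duplicated; at a CV of 5% to 10% a drop of more than 30% occurs in at most 0.6% of duplicates. The upward bias needs independent results with equal error. In the single-subject example nothing shows that +168% is further from the truth than +212%. Both results are in the data, so the discordance is visible; what is missing is an instruction to act on it.

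All of this stands, and it limits the point to a correction of the text. It does not remove the point: the SAP gives one definition, that definition is signed, and a programmer who follows it gets the one-sided rule. Absolute-value bars could have been lost when the PDF was read, but the parentheses survived and nothing suggests a missing symbol.

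**Conclusion.** The concern holds, as a minor one. That the printed rule is one-sided and order-dependent is certain from the text. Its effect on results is not known, because it depends on the unstated number of duplicates, the unstated assay CV and an unseen program. Under the assumed CVs, with equal duplication in both subgroups, the effect on the subgroup contrast is at most 0.05 of the planned standard error and nearly cancels if both visits are duplicated. Nothing links duplication to amyloid status, so no differential bias is claimed. The practical exposure is a single discordant value kept in a subgroup of about 6.

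**What to change.** In SAP 8.2.3, define the deviation as 100% × |second result - first result| / first result, keep the 15% and 30% limits, and confirm that the derivation program matches.

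Dividing by the mean of the pair is optional. It makes the tier independent of assay order (100 then 72 and 72 then 100 are both missing), but tier 1 would still report whichever result came first.

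The cost is more averaged or missing values. Missing among duplicated samples, as printed against absolute value, is 0.0 v 0.0% at CV 5%, 3.1 v 3.7% at 10%, 10.7 v 15.2% at 15% and 17.5 v 27.6% at 20%. That is one extra missing value per about 22 duplicated samples at CV 15% and per about 10 at CV 20%. No imputation of PD data is described, so each missing cGMP value may remove a subject from the primary model. Losing 1 of 6 in one subgroup raises the standard error from 34.6 to 60 × sqrt(1/5 + 1/6) = 36.3, or 5%. Those extra missing values come from the discordant pairs that tier 3 was evidently meant to remove.

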8.3 Safety data handling

8.3.1 Baseline Safety

The baseline value for all safety endpoints will be the last non-missing measurement occurring prior to the first dose of the study medication.

8.3.2 Treatment Duration for Safety Analyses

The treatment duration for all safety variables is considered to begin on Day 1 and ends 28 days after the last dose of study medication. Treatment emergent safety data (ie labs, vital signs and ECGs) are defined as observations that were recorded during treatment or within 28 days following the last dose of study drug, these will be flagged in the listings as “off treatment, but treatment emergent”. This data will be windowed and summarized as described below. Data after 28 days of last dose will be flagged as post TE and listed only.

For summaries of safety by time points, the time points will be relative to date of first dose. For standardized reporting, study day windows relative to the first dose (Day 1) in the study will be applied to determine into which week the data will be mapped. All pretreatment assessments are conducted during Screening/Baseline Periods before Day 1. The Analysis Baseline is the last non-missing pretreatment assessments. Scheduled, unscheduled, and early discontinuation visits will be mapped to weeks. Table 5 gives the mapping of relative day ranges to week for non-AE safety variables. If a subject did not have a recorded

observation falling within a given range of days in order to be assigned to a week, the subject's data for that week will be regarded as missing for summarization purposes. If there are 2 or more assessments in the same window, the following rules will be used:

- If the window is for the screening/baseline assessment, then the latest assessment will be used in the summary tables;
- If the window is for the follow-up assessment, then the latest assessment will be used in the summary tables;
- If the window is not for the screening/baseline or the follow-up assessment, then the assessment closest to the scheduled assessment will be used in the summary tables. Note that if 2 assessments are equidistant from the scheduled assessment then the last assessment of the 2 (within the allowable window) will be used.

Table 5 Mapping of Study Day Ranges to Week for Safety

Windowing Period	Study Day Range (Relative to First Dose)	Week
Screening	$(-42) \leq \text{Day} \leq (-8)$	
Baseline	$(-7) \leq \text{Day} \leq (-1)$	
Analysis Baseline	-	a
Treatment	$1 \leq \text{Day} \leq 32$	3
Treatment	$33 \leq \text{Day} \leq 53$	6
Treatment	$54 \leq \text{Day} \leq 74$	9
Treatment	$75 \leq \text{Day} \leq 98$	12 (d)
End of Treatment (EOT)	-	b
Follow up	Follow up visit	c

a: All pretreatment assessments are conducted during Screening/Baseline Periods before Day 1. The Analysis Baseline is the last non-missing value measured during pretreatment phase.

b: For completer, EOT is the Week 12 visit. For early discontinuation, EOT is the Early Discontinuation (ED) visit. If the above visits are missing, then the last non-missing value collected not later than 7 days after the last dose will be used.

c: If follow up visit is missing, there will be no imputed follow up visit.

d: For assessments with no Week 3/6/9 planned assessments (ie UPDRS), the window for the Week 12 assessment is $1 \leq \text{Day} \leq 98$. The data must be within in the date of first dose and date of ED visit (for early discontinuation subjects). For completers, date of last dose is irrelevant, window the visit based on study day range in above table. For Lab data (and other similar data) where only Week 6 and 12 are performed, the window for Week 6 is $1 \leq \text{Day} \leq 53$, and Week 12 the window is $54 \leq \text{Day} \leq 98$.

For subject visits after the treatment emergent period (not defined as a CRF follow up visit) will be labelled as Post TE and listed only.

